11. 0.76	12. 0.38	13. 0.01	14. 0.9	15. 48
16. 0.76	17. 0.38	18. 0.05	19. 0.9	20. 34

Although our sample size has been designed based on the frequency of hypoventilation in patients during the PACU stay, we have also estimated the power that a sample size of n=40 patients per group would have to detect a difference on the incidence of residual NMB. In a preliminary sample of 25 patients after general anesthesia and neostigmine used for NMBR at our institution, 9 patients had a quantitative TOF T4/T1 <0.9 in the PACU (36%). This matches the incidence range 10-50% of TOF <0.9 observed in other studies[8, 10, 49]. The reported frequency of qTOF <0.9 after 15min of

sugammadex administration in other surgical populations is <8%[34, 39, 50, 51]. With this incidence of residual NMB, our proposed sample size would have 90% power to detect a reduction to residual NMB to an incidence of 5% (alpha 0.05):

G. Summarize Knowledge to be Gained

This study will fill an important gap of knowledge with immediate clinical applications: 1) determine the efficacy of sugammadex, compared to neostigmine, for NMBR in patients with severe kidney dysfunction undergoing a kidney transplant; and 2) characterize the effect of sugammadex and neostigmine on postoperative ventilation, dependent and independent to residual or recurrent NMB and other contributing factors (e.g. opioids). Our study will describe the effect of NMBR on objective and quantitative assessments of qTOF and minute volume ventilation. Additional measures will include patient's subjective dyspnea scores (with a validated questionnaire), PPCs and kidney graft outcomes, hospital resource utilization and estimated healthcare costs.

H. References

- 1. Fuchs-Buder, T., R. Nemes, and D. Schmartz, *Residual neuromuscular blockade: management and impact on postoperative pulmonary outcome*. Curr Opin Anaesthesiol, 2016. **29**(6): p. 662-667.
- 2. Hayes, A.H., et al., *Postoperative residual block after intermediate-acting neuromuscular blocking drugs*. Anaesthesia, 2001. **56**(4): p. 312-8.
- 3. Fortier, L.P., et al., *The RECITE Study: A Canadian Prospective, Multicenter Study of the Incidence and Severity of Residual Neuromuscular Blockade*. Anesth Analg, 2015. **121**(2): p. 366-72.

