Additional outcomes will include: intraoperative minutes from NMBR administration to qTOF T4/T1 >0.9 , to extubation, and total in operating room time; incidence of residual NMB in PACU based on qTOF; number of events and accumulated minutes of hypoventilation in PACU; frequency of patients with ≥ 1 events of delayed postoperative hypoventilation (daily for up to 3 postoperative days) and accumulated minutes of hypoventilation; delayed recurrence of NMB based on qTOF; presence of pre-defined postoperative pulmonary complications during hospital stay and by the postoperative day 14 ± 3 ; standardized Patient-Reported Outcomes Measurement Information System (PROMIS®) dyspnea functional limitations questionnaire score compared to patient's baseline; pre-defined kidney graft outcomes; hospital resources utilization (e.g. hospital length of stay, ICU admission) and their cost estimates.

[figure not shown]
B. Description of Population to be Enrolled

We will include adults (≥ 18 years and ≤ 90) diagnosed with severe kidney dysfunction (defined by plasma creatinine clearance <30 mL/min) and planning on kidney transplantation surgery at the University of Colorado Hospital. Exclusion criteria: patients unable to sign the informed consent, pregnant women, Body Mass Index (BMI) > 40 , pre-existing oxygen or ventilatory dependency (24h use of oxygen or other noninvasive or invasive ventilatory support), or patients with any pulmonary, neuromuscular or other disease that severely limits their respiratory functional status (e.g. unable to achieve 4 Metabolic Equivalent of Tasks, METs, such as climbing up 1 flight of stairs[32]), or any contraindication for any of the study-related medications or interventions.

C. Study Design and Research Methods

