We have designed a prospective randomized double-blind single center study on 100 patients with severe kidney failure undergoing kidney transplantation surgery. Patients will be randomized to receive either NMB with rocuronium and sugammadex for NMBR (intervention group) or NMB with rocuronium and neostigmine for NMBR (control group). Respiratory function will be objectively monitored starting in PACU and during the first 3 postoperative days or until end of monitoring criteria are met. A blinded assessor will record the frequency of hypoventilation events as well as the accumulated minutes of hypoventilation. Quantitative TOF monitoring will be evaluated by a blinded investigator. Additional data related to patient's comorbidities, morphine equivalents (mg/kg) received, validated dyspnea patient-reported scores, pulmonary complications, kidney graft relevant data and outcomes, and hospital resource utilization and estimated costs will also be collected.

After signing informed consent, patients will be randomized to receive, during kidney transplant surgery, NMB with rocuronium and NMBR with either sugammadex (intervention group) or neostigmine (control group). Both groups will receive intraoperative NMB agents and reversal medications as guided by qTOF monitoring and following FDA-approved doses (see details below). In the PACU, we will perform continuous monitoring of their MV during their PACU stay and assess qTOF at selected time points in all patients. Institutional discharge criteria from PACU is based on an Aldrete's score[33] ≥ 8 assuming there are no discharge concerns by the patient's healthcare providers (PACU nurse, anesthesiologist and/or surgeon). After discharge from PACU and during the first 3 postoperative days (or until end of monitoring criteria if sooner) we will maintain the continuous MV monitoring and daily quantitative TOF assessment, collect opioids received and data relevant to pulmonary complications, kidney graft outcomes and estimated healthcare costs. At the postoperative surgery clinic visit or by phone interview we will collect patient's subjective dyspnea scores and compare to their baseline (with a validated questionnaire), as well as updated PPCs, kidney graft outcomes, hospital resources utilization and estimated healthcare costs.

Preoperative phase

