Screening for eligibility and consenting will take place once the patient has been accepted for kidney transplantation at the University of Colorado Hospital by the Transplant Surgery team. Randomization will occur after patients consent for the study. Only the PI will remain unblinded to the group allocation (see below).

Preoperative data will be collected by the blinded investigator (study coordinator), including baseline vital signs (including room air SpO₂), comorbidities, medications, and kidney graft relevant factors. The baseline dyspnea scores will be assessed by asking patients to complete the PROMIS® v1.0 Dyspnea Functional Limitations Short Form 10a_9-2-2016 questionnaire (available at http://www.healthmeasures.net/administrator/components/com_instruments/uploads/PROMIS%20SF%20v1.0-Dyspnea%20Functional%20Limitations%2010a_9-2-2016.pdf). This is a validated and standardized short questionnaire to quantitate if sugammadex used for NMBR reduces the subjective dyspnea scores relative to baseline.

Intraoperative phase

We will perform a prospective parallel randomized study of rocuronium/sugammadex (intervention) vs. rocuronium/neostigmine (control) for NMB and NMBR at the end of kidney transplantation surgery. This will be performed by the unblinded investigator, following the following protocol(s):

- A quantitative TOF (qTOF) monitor (the Stimpod NMS450®, Xavant Technology Ltd., South Africa, the acceleromyography-based monitor available at UCH, and/or the TwitchView™, Blink Device Company, Seattle, WA, an electromyography-based monitor) will guide the NMB and NMBR management in all study patients. Quantitative NMB monitoring are considered superior to the more routinely-used but subjective qualitative TOF monitors[34, 35]. The qTOF monitor will be placed in the ulnar nerve territory to stimulate the adductor pollicis muscle[36] immediately after loss of consciousness during induction of anesthesia. The exact location of monitoring will be marked and used for qTOF measurements in the postoperative period.
- NMB brief protocol: Rocuronium will be the NMB agent used in both groups as guided by the qTOF and following standard dosing protocols in order to achieve adequate NMB to allow the intubation and surgical procedure (routinely T4/T1 < T3 until closure of surgical incision). Rocuronium dosing: 0.6-1.2 mg/kg for intubation, 0.08-0.2 mg/kg bolus for maintenance with recovery of second twitch (T2) in qTOF.

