- NMBR brief protocol: The sugammadex (intervention) or neostigmine (control) will be administered at the end of the surgery. The goal will be to administer the appropriate NMBR medication when ≥ 2 twitches are objectivized with the qTOF monitor. NMBR drugs and dosing for each group will follow standard of care FDA-approved doses, as follows: Sugammadex 2 mg/kg will be administered when spontaneous recovery has reached the reappearance of the second twitch in response to TOF stimulation.

	Sugammadex dosing (mg/kg)	Neostigmine dosing (mg/kg)
T4 recovered	2	0.03-0.05 (max 5 mg)
T2/T3 recovered	2	0.05-0.07 (max 5 mg)
T0/T4 with 1-2 post-tetanic twitches present or T1 recovered	4 or wait	Wait

Overdosing of neostigmine will be avoided to prevent neostigmine-induced muscle weakness. Neostigmine will be administered simultaneously with the appropriate glycopyrrolate dose (0.2 mg per 1.0 mg of neostigmine).

Extubation will be performed following the usual standard of care criteria of adequate level of consciousness, presence of airway protection reflexes and spontaneous ventilation parameters in addition to quantitative TOF $T4/T1 >0.9$. The following times (minutes) will be recorded: NMBR administration-to-T4/T1 >0.9 , NMBR administration-to-extubation, total operating room time.

Postoperative in-hospital phase

The blinded investigator will collect the following study-related information:

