- **Discomfort during neuromuscular blockade monitoring:** Monitoring of NMB with a Train-Of-Four (TOF) monitor consists of provoking muscle twitches that can be uncomfortable in awake patients, proportionally to the amplitude of the electrical signal used. In awake the TOF monitoring is usually well tolerated at 30-40 mA, which is the amperage we are planning on using. This has been used without problems by us and others[3, 29, 39], but we will reduce the amperage if uncomfortable for a study patient.
- **Risk to privacy:** There is a small risk of loss of privacy of confidential data collected from study participants. We will collect the minimum patient information required for the study and use RedCap for data collection and storage. The paper copies of study data and the electronic master file will be stored behind locked doors in the PI's office and protected by the security measures established by the University of Colorado network.

E. Potential Scientific Problems:

This study has been designed to detect differences in the incidence of hypoventilation (primary outcome) but the sample size may be insufficient to detect differences in clinically relevant complications secondary to hypoventilation. Such a study would require a larger study sample.

F. Data Analysis Plan:

The investigator and statistician will be responsible for analyzing the study data. The PI will be unblinded in order to follow the intraoperative study protocol. The study coordinator will be blinded to the randomization allocation, and will be responsible for performing the preoperative (baseline) and postoperative assessments. The official clinical database will not be unblinded until the data is clean and complete and the last independent safety review has been performed, and the study database is locked. The groups will be blindly labeled in the study website and only the PI and the safety review monitor will have access to the group codes.

Variables/Time Points of Interest

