Incidence of residual or recurrent NMB in the postoperative floor. This will be calculated as described before (T4/T1 <0.9 , considered severe if T4/T1 <0.4), as an average of 3 repetitions obtained on two occasions separated by ≥ 6 h daily on postoperative days 1-3 or until the end of monitoring criteria have been met.

Morphine equivalents will be calculated from individual opioid doses administered to each patient following standard conversion formulas[21, 40]. This morphine equivalent dose will be calculated for the PACU period and daily for 3 first postoperative days or until the end of monitoring criteria have been met, and used as covariate in the logistic regression analysis.

Time from NMBR administration to quantitative TOF T4/T1 >0.9 (minutes, one decimal). The quantitative TOF will be repeated at 80 mA every 30 seconds from the moment the NMBR medication (sugammadex or neostigmine) has been completely administered intravenously.

Time from NMBR administration to extubation (minutes, once decimal).

Time of total operating room time (minutes), counting from in-room time stamp to out-of-room time stamp.

The PROMIS® v1.0 Dyspnea Functional Limitations Short Form 10a_9-2-2016 questionnaire is a validated and standardized short questionnaire to quantitate if sugammadex used for NMBR reduces the subjective dyspnea scores relative to baseline. It will be completed by the patient in the preoperative phase and during the postoperative follow up. It is available at http://www.healthmeasures.net/administrator/components/com_instruments/uploads/PROMIS%20SF%20v1.0-Dyspnea%20Functional%20Limitations%2010a_9-2-2016.pdf.

Postoperative Pulmonary Complications (PPCs) following previous definitions[13, 41, 42], including:

Respiratory Failure, defined as[41]: "When postoperative $\text{PaO}_2 < 60\text{mmHg}$ on room air, a ratio of PaO_2 to inspired oxygen fraction < 300 or arterial oxyhemoglobin saturation measured with pulse oximetry (SpO_2) $< 90\%$ and requiring oxygen therapy".

Unplanned intubation with postoperative mechanical ventilation (POMV), defined as placement of a breathing tube that was not intended or planned, excluding instances of intubation during an unplanned return to the operating room. Also excluded those patients that were transferred intubated and ventilated to the intensive care unit (ICU) from the operating room.

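### The unrestricted statement that quantitative TOF is evaluated blind does not cover the operating-room readings behind time to T4/T1 >0.9

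*Combined protocol and SAP*

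**What the plan says.** The overview in III.C (Study Design and Research Methods) states: "Quantitative TOF monitoring will be evaluated by a blinded investigator". The sentence carries no restriction to a phase or location.

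The detailed text divides the work by phase:

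- **Who is unblinded.** III.C, Preoperative phase: "Only the PI will remain unblinded to the group allocation (see below".
- **Operating room.** III.C, Intraoperative phase, on the comparison of the two reversal strategies: "This will be performed by the unblinded investigator, following the following protocol(s". The first item of that protocol is the TOF monitor, which "will guide the NMB and NMBR management in all study patients".
- **Reason for unblinding.** III.F, Data Analysis Plan: "The PI will be unblinded in order to follow the intraoperative study protocol". The same paragraph gives the blinded coordinator the assessments before and after surgery.
- **After surgery.** The blinded investigator's list of tasks opens with the Postoperative in-hospital phase. The TOF readings on it are those in the PACU and on the floor.

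The outcomes concerned appear in III.A (Outcome Measures) as "intraoperative minutes from NMBR administration to qTOF T4/T1 >0.9 , to extubation, and total in operating room time". The end of the Intraoperative phase says: "The following times (minutes) will be recorded: NMBR administration-to-T4/T1 >0.9 , NMBR administration-to-extubation, total operating room time". Under Variables/Time Points of Interest in III.F, "Time from NMBR administration to quantitative TOF T4/T1 >0.9" is defined from readings at 80 mA every 30 seconds once the reversal drug is in. Neither place names the person who reads or records.

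**The concern.** Time to T4/T1 >0.9 is the most direct measure of reversal among the listed outcomes. The background section already expects neostigmine to be slower and less effective. If the person reading the monitor knows the arm, that expectation can affect whether a doubtful value is repeated and which crossing of 0.9 is written down.

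The definition leaves room for this. It fixes the current and the interval, but not whether the first value above 0.9 counts or whether it must be confirmed. The PACU assessment, by contrast, averages three repetitions against a cut-off.

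What is at stake is how the result is read. A report that repeats the III.C sentence would present recovery time as a blinded measurement when the described procedure does not make it one.

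**Working it through.** The plan gives no figure to reproduce. The check sets the sections side by side.

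**Step 1: which TOF readings have a blinded assessor?**

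| Readings | Assigned to | Where stated |
|---|---|---|
| Operating room, guiding blockade and reversal | Unblinded investigator | III.C Intraoperative phase; III.F Data Analysis Plan |
| Operating room, every 30 s after reversal | Nobody named | III.F Variables/Time Points of Interest |
| PACU, on arrival and hourly | Blinded investigator | III.C Postoperative in-hospital phase |
| Floor, twice daily | Blinded investigator | III.C Postoperative in-hospital phase |

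The second row has to be inferred. The 30-second readings belong to the intraoperative phase, which is given to the unblinded PI. The blinded coordinator is given only the phases before and after it, and no other assessor is mentioned. The natural reading is that the arm is known when these values are taken. This is an inference, not a statement in the protocol.

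**Step 2: which of the three operating-room times does the III.C sentence cover?**

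- *Time to T4/T1 >0.9:* a TOF measurement, so it is covered by the sentence as worded.
- *Time to extubation:* depends partly on T4/T1 >0.9, but also on consciousness, airway reflexes and ventilation. The sentence does not claim blinding for it. The documents do not say who decides on extubation or whether that person knows the arm.
- *Total operating room time:* defined by in-room and out-of-room time stamps, which leaves little to assessor judgement. The sentence does not cover it.

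**Step 3: what can be said about size?**

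The only relevant figure in the documents is the 30-second interval.

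- One reading earlier or later: 30 s / 60 = 0.5 min for that patient.
- Two readings: 2 × 0.5 = 1.0 min for that patient.

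If a fraction f of an arm moved by one reading in the same direction, the arm mean would move by f × 0.5 min. That is 0 min at f = 0 and 0.5 min at f = 1. The documents give nothing from which f, its direction or the expected difference between arms could be set, so no bias estimate follows.

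**Step 4: does it reach the primary analysis?**

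No. Hypoventilation comes from the respiratory volume monitor with a blinded assessor, and the TOF covariate in the logistic model comes from the PACU readings, which are assigned to the blinded investigator. The Multiplicity section calls secondary analyses exploratory, and Statistical Methods specifies no model for the operating-room times.

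**The case against.** The strongest reply is that the III.C sentence is a summary line that the protocol itself resolves. It follows text on monitoring from the PACU onward, the detailed sections then assign PACU and floor TOF to the blinded investigator, and the PI's unblinding is stated openly more than once. On this view the sentence is over-general, not contradictory. That is a fair reading, and it limits the severity. It does not supply a blinded assessor for recovery time, and the sentence as written still claims more than the design provides.

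A second reply is that T4/T1 is a number from a device, compared with a fixed threshold at a fixed current and interval. This also stands in part. The discretion that remains is over repeat readings and over first versus confirmed crossing. The latter is a question of endpoint definition that blinding alone would not settle.

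A third is that dosing differs by arm and by twitch count, so an unblinded operator is a reasonable choice. I agree; the point concerns the description and the derivation, not that choice.

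Three stronger readings are tempting and are not supported:

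- *The stated blinding fails for all three operating-room times.* The sentence concerns TOF only, so it can fail for at most one of them.
- *The protocol says the unblinded investigator takes the recovery readings.* It names no recorder; this is inferred.
- *The bias is a sizeable share of recovery time.* With an assumed mean of 2 to 3 min in the faster arm, one could compute 0.5 / 3 = 17% up to 1.0 / 2 = 50%. The mean is not in the documents, the two ends pair opposite extremes, and the shift would have to occur in every patient of the arm in one direction. The quantity that matters, the difference between arms, is not given either.

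**Conclusion.** The point holds in a limited form. The blinding stated for quantitative TOF does not extend to time from reversal to T4/T1 >0.9. This rests on one inference: that whoever runs the intraoperative protocol also reads the monitor during it. Extubation time shares the lack of a named blinded assessor and is more open to judgement, but the protocol makes no contrary claim about it. Operating room time is little exposed.

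The effect is at most 0.5 min per discretionary reading in an individual patient, and its effect on the comparison between arms is unknown. The severity is minor: an exploratory outcome is affected, and no confirmatory conclusion is.

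**What to change.** 1. In III.C, limit the blinding sentence to TOF assessed in the PACU and on the floor.
2. In III.F, under the definition of recovery time, require every 30-second T4/T1 value to be kept with its time. Use the monitor log if it can be exported (the documents do not say that it can), otherwise the case form.
3. State one rule in advance for the time to >0.9, either first crossing or confirmed crossing. Have the blinded coordinator or the statistician apply it to values stripped of arm labels.
4. Name who takes and records the intraoperative readings. Report time to >0.9 as measured by an unblinded operator and derived blind, and extubation time as not assessed blind.

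These are wording changes and the retention of readings already planned, with no added staff. The cost is a slightly longer case form and a more modest blinding claim. The remedy is partial: it removes discretion over which value is chosen, but not over which readings an unblinded operator takes or, where the case form is used, writes down.

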The secondary analysis comparing delayed efficacy of sugammadex to neostigmine in reducing the incidence of hypoventilation during the first 3 postoperative days will assume the same model and covariates as the primary hypothesis. To compare the incidence of PPCs a logistic regression model will be used with the binary outcome of any PPC and will include covariates for group and total morphine equivalents. Hospital length of stay and costs will be compared between groups using a linear regression model including covariates for group, total morphine equivalents, presence of respiratory comorbidities and other clinical differences that may influence the outcome. Continuous outcomes may be transformed if they violate the normality assumption (e.g., a log-transformation).

Multiplicity

Given only one primary outcome and hypothesis, there is a not a concern for multiplicity. Secondary analyses are considered exploratory in this protocol.

Power/Sample Size:

Based upon a sample size of 40 patients per group, this study has 90% power to detect a 50% difference in hypoventilation incidence in the PACU (from 76% as reported in previous studies[21] to 38%, alpha 0.05), assuming a potential dropout of up to 6 patients per group. The 50% reduction is considered clinically relevant for a decrease in the frequency of hypoventilation, a precursor of more clinically significant complications such as hypoxemia, reintubation or pneumonia. Quantifying the contribution of hypoventilation into more severe complications is challenging, and details of duration and severity of hypoventilation are not well known. Thus, only a significant reduction in hypoventilation incidence (i.e. 50%) may be accepted as relevant. This trial will provide additional detailed information that may provide more insight on the clinical consequences of hypoventilation (e.g. potential association between accumulated minutes of MV <40% expMV and decrease in SpO₂/FiO₂ over the following 30 min).

A sample size of 40 patients per group would also have approximately 80% power (78%) to detect a difference in case the incidence of any hypoventilation events is 60%, instead of the literature-based 76%. The table below provides the sample size per group to achieve a variety of assumptions for the primary outcome, alpha, and power:

Incidence Group 1	Incidence Group 2	Alpha	Power	Sample Size per Group
1. 0.76	2. 0.38	3. 0.01	4. 0.8	5. 39
6. 0.76	7. 0.38	8. 0.05	9. 0.8	10. 26

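### The investigator who runs the rocuronium protocol already knows the arm, so depth of block at reversal can differ between arms for reasons other than the study drug

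*Combined protocol and SAP*

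**What the plan says.** Section III.C, Preoperative phase, sets the order of events. On consent: "Screening for eligibility and consenting will take place once the patient has been accepted for kidney transplantation". On allocation: "Randomization will occur after patients consent for the study". No interval is given between consent and randomisation, or between randomisation and surgery.

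The Intraoperative phase of III.C introduces its steps with "This will be performed by the unblinded investigator, following the following protocol(s"). The steps that follow cover quantitative train-of-four (qTOF) monitoring, rocuronium and reversal. Section III.F gives the reason for the unblinding: "The PI will be unblinded in order to follow the intraoperative study protocol". The dosing text reads: "Rocuronium dosing: 0.6-1.2 mg/kg for intubation, 0.08-0.2 mg/kg bolus for maintenance with recovery of second twitch (T2) in qTOF".

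Sugammadex or neostigmine is given only at the end of surgery. Reversal at two or more twitches is worded as a goal. In the deepest-block row of the reversal table, the sugammadex entry permits a dose or waiting, while the neostigmine entry permits only waiting. Nothing in the documents conceals the allocation until reversal or gives the rocuronium decisions to a blinded person.

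**The concern.** Until reversal, the two arms should be managed identically. Here the person running the block knows which reversal drug will follow, and has room to act on it.

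The reversal table also supplies a motive. A deep block at closure can be reversed at once in one arm but means a delay in the other. An investigator who knows this may, without intending to, let the block lighten earlier in the neostigmine arm or keep it deeper in the sugammadex arm.

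A recovery time that starts at reversal depends on the depth of block at that moment. A difference in depth created by the investigator would then be read as a drug effect, or would hide one. The list of variables in III.F contains neither total rocuronium dose nor twitch count at reversal, so an imbalance could not be seen afterwards.

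**Working it through.** **1. How much room the rocuronium ranges leave (III.C, Intraoperative phase)**
- Intubation: 1.2 / 0.6 = 2-fold.
- Maintenance bolus: 0.2 / 0.08 = 2.5-fold, given when the second twitch returns.

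The agent, ranges and trigger are the same in both arms. The choice within each range is not blinded.

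**2. Which outcomes are exposed**
- *Time to T4/T1 >0.9 and time to extubation.* Both run from reversal. III.F starts the first clock once the reversal drug has been fully given. No later safeguard protects these times from a difference in starting depth.
- *Residual block in the PACU.* Measured after extubation, for which T4/T1 >0.9 is required in both arms. Partly protected.
- *Hypoventilation in the PACU (primary).* Monitoring starts on PACU arrival, after the common extubation threshold, and the assessor is blinded. Exposure is indirect.

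The primary model adjusts for train-of-four response. As described in III.F, that covariate is measured in the PACU, after the study drug, so it does not stand in for depth of block before reversal.

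**3. Does loss before study drug threaten power?**

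Inputs from Power/Sample Size: 76% versus 38%, alpha 0.05 (taken as two-sided), 90% power, 40 per group, "assuming a potential dropout of up to 6 patients per group".

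Reproducing the plan's figure, with pooled proportion (0.76 + 0.38)/2 = 0.57:

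n = [1.96·√(2 × 0.57 × 0.43) + 1.2816·√(0.76 × 0.24 + 0.38 × 0.62)]² / 0.38²
= [1.96 × 0.7001 + 1.2816 × 0.6465]² / 0.1444 = 33.5, rounded up to 34.

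This matches the table. The allowance is 6/40 = 15%, and 34/(1 − 0.15) = 40. Power by the same formula:

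| Evaluable per group | Loss from 40 | Power |
|---|---|---|
| 40 | 0% | 94.5% |
| 34 | 15% | 90.4% |
| 32 | 20% | 88.5% |
| 28 | 30% | 83.8% |

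The stated allowance holds power at about 90%, so power is not the problem.

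**4. What a titration bias could do (illustration only)**

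The documents give no figure for the effect of block depth on hypoventilation. Assume no drug effect, and let arm-dependent depth alone lower the risk in one arm from 76%. With 40 per group and an unadjusted two-sided 5% test, the false-positive rate is Φ[(d − 1.96·SE₀)/SE₁] + Φ[(−d − 1.96·SE₀)/SE₁], where d is the shift and SE₀ and SE₁ are the pooled and unpooled standard errors. For d = 0.10: SE₀ = √(2 × 0.71 × 0.29/40) = 0.1015 and SE₁ = √((0.76 × 0.24 + 0.66 × 0.34)/40) = 0.1008, which gives 16.5%.

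| Assumed shift | False-positive rate |
|---|---|
| 5 points | 7.9% |
| 10 points | 16.5% |
| 15 points | 30.1% |

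The shifts have no source in the documents. The table shows sensitivity and is not an estimate.

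**The case against.** The case against is substantial. Rocuronium is guided by qTOF, with the same agent, ranges and trigger in both arms. Both arms share the two-twitch goal, and both must exceed T4/T1 0.9 before extubation. The primary outcome begins only afterwards and is assessed blind. The recovery times are not primary, and the plan calls its secondary analyses exploratory. All of this stands, and it moves the exposure away from the primary outcome. It does not protect the recovery times.

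The differing deep-block entries can also be seen as part of the strategies being compared. A difference in depth that follows from that written rule is not investigator bias. This stands too, and later release of the allocation would not remove it. What later release removes is knowledge of the arm while rocuronium is being given.

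Three stronger readings are tempting and are not supported:
- *That 20 to 32 of 100 randomised patients will fall outside the analysis, mostly before study drug.* The figures come from setting "prospective randomized double-blind single center study on 100 patients" against the sample size section: 100 − 2 × 40 = 20 and 100 − 2 × 34 = 32. The documents do not explain that gap or call it loss after randomisation, and they give no reasons or timing for dropout. The only stated allowance is 6 per group, or 12 of 80.
- *That losses before study drug break the comparison.* Patients are to be managed alike up to reversal, and only the principal investigator and the safety monitor hold the codes. Such losses are unlikely to depend on arm and mainly cost efficiency.
- *That patients are randomised at the moment of consent.* The text says only that randomisation comes after consent, so the day of surgery is possible.

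**Conclusion.** The point holds as a weakness in when the allocation becomes known. An investigator who knows the arm carries out the rocuronium protocol within 2- to 2.5-fold ranges before the arms are meant to differ, and nothing in the plan conceals the allocation until reversal. The threat is mainly to time to T4/T1 >0.9, time to extubation and residual block. An effect on the primary outcome is limited, though not excluded.

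Its size cannot be derived from the documents, and neither can the number of patients randomised but never reversed. The conclusion rests on reading the intraoperative section literally, with the unblinded investigator making or directing the rocuronium decisions. If a blinded clinician in fact makes them, the protocol should say so and most of the concern falls away. This is a worthwhile, low-cost improvement and not a fatal flaw.

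**What to change.** Keep consent as it is. Assign the allocation, or at least reveal it to the principal investigator, only at wound closure when reversal is about to be prepared, through the study database or a sealed envelope. Record the twitch count just before the allocation is opened and the total rocuronium dose, and report both by arm.

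Assigning at that point is the better option, because it also avoids most losses before study drug. Late reveal alone leaves those losses in place but keeps arm knowledge out of rocuronium titration.

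Separately, the investigators must reconcile the differing deep-block entries in the reversal table with the goal of at least two twitches. Later release of the allocation does not settle that.

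The cost is a short amendment, drug preparation a few minutes later and two extra data items. The sample size inputs and the consent process do not change.
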